## 12. Study Population

#### 12.1. Describe inclusion criteria.

Parents: Parents must be English speaking, ≥18 years old, have a newborn singleton infant ≤2 months, born at ≥35 weeks gestation who is receiving pediatric care at an enrolled Seattle area clinic or Group Health clinic, and be vaccine hesitant (defined as ≥2 positive responses on questions 1, 3, 6 and 8 on the eligibility screening survey (Appendices F and P); these questions constitute the PACV-SF).

Newborns: Newborns 0 - 2 months old whose parents enroll in the study will be included.

Providers: All Seattle area primary care practices and Group Health primary care clinics within a 5 county region in western Washington (Snohomish, King, Pierce, Thurston, and Kitsap Counties) will be eligible to participate. Once clinic leadership has agreed to participate, all pediatric and family practice providers (MD, DO, ARNP, PA-C) at those clinics will be eligible to participate.

#### 12.2. Describe exclusion criteria.

Parents/Children: Parents who are not 18 years or older, require language interpretation for medical care, have an infant born <35 weeks gestation, are not vaccine hesitant or will not be taking their child to a participating clinic for health supervision visits will be excluded.

Providers: Clinics and providers outside the Seattle area or 5 county region in western Washington (Snohomish, King, Pierce, Thurston, and Kitsap) will be excluded.

#### 13. Study Procedures

This section should list the procedures, observations, measures, etc. at each study visit, including history, examination, study drug administration or other interventions (can be provided in table form as a Table of Evaluations often used in protocols).

13.1. **Describe study visits.** Parents will be approached and screened for this study by a research assistant (RA) over the telephone (Group Health parents only) or at their child's clinic upon check-in for their child's health supervision visit that occurs at or before 2 months of age. For Group Health parents who are screened over the telephone, an RA will meet the parent at their child's 2 month health supervision visit to complete the consent and enrollment process. This enrollment encounter will include having the parents who are eligible and agree to participate complete the demographic survey (Appendix G). If enrollment occurs at a health supervision visit prior to 2 months of age, an RA will meet the parent back at their child's clinic at the time of their child's 2 month health supervision visits to have them complete an electronic version of the study survey using an iPad® (i.e. the intervention survey at SPARCK clinics (Appendix A) and the placebo survey at control clinics (Appendix B)). If enrollment occurs at the 2 month health supervision visit, the RA

Study Title: Screening Parents about Recommended

Care for Kids (SPARCK) Study

Principal Investigator: [name], MPH

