**Version Date: 5/1/2018** 

Name of Questionnaire/Instrument	How will the questionnaire/instrument be administered? (Examples: study personnel, self-administered, computer, etc.)	Who answers the questionnaire? (Examples: parent, child)	If modified after initial approval, note current revision date:
Parent SPARCK intervention survey (Appendix A)	Self-administered on iPad®	Parent	
Parent SPARCK Placebo Survey (Appendix B)	Self-administered on iPad®	Parent	
Parent post-visit satisfaction survey (Appendix E)	Self-administered on paper	Parent	
Parent Eligibility Survey (Appendix F)	Study personnel verbally	Parent	
Parent demographic survey (Appendix G)	Self-administered on paper	Parent	
Provider Baseline Survey (Appendix K)	Self-administered electronically	Provider	
Provider Follow-Up Survey (Appendix L)	Self-administered electronically	Provider	
Vaccine data collection form for Allegro Pediatrics sites	Study personnel	Study personnel	

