**Version Date: 5/1/2018** 

#### **Investigator Help**

## 11. Investigational Plan

## 11.1. Describe the general schema of the study design.

Figure 1. Study Design

This study is a cluster randomized controlled trial. We will pair up to 30 Seattle area primary care clinics and Group Health primary care clinics based upon the number of vaccine doses ordered and enroll and randomize clinics to control and SPARCK arms. We will screen parents for vaccine hesitancy using the Parent Attitudes about Childhood Vaccines Short Form survey (PACV-SF) (Appendix F). Parents in the SPARCK arm of the study will take the intervention survey (which has the PACV embedded in it) to their child's 2 and 6 month visits (Appendix A) whereas parents in the control arm of the study will take a placebo survey about childhood health topics (Appendix B). The results of these surveys will be communicated to the child's provider (Appendices C and D). After the child's 6 month visit, parents in both arms will complete a satisfaction survey about their visit experience (Appendix E). When the child is 8 months of age, we will use an automated clinic immunization database to determine their immunization status. For participants who were lost to follow up (i.e. those who did not have a 6 month appointment, or those who did not have a 2 and 6 month appointment), we will also use Washington State Immunization information System records to determine participant immunization status.

Study Title: Screening Parents about Recommended

Care for Kids (SPARCK) Study

Principal Investigator: [name], MPH

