**Version Date: 5/1/2018** 

will simply proceed to administer the intervention or placebo survey right after enrollment. The RA will generate and print an automated summary sheet of the parent's screening results, and hand the printed summary sheet to the child's provider before the visit begins (Appendices C and D). They will also alert the provider that their patient is a SPARCK study participant by writing, "SPARCK STUDY" in the scheduling notes section of the child's electronic health record. This process will be repeated before the child's 6 month health supervision visit. After their child's 6 month health supervision visit, parents will complete a survey about their satisfaction with their child's provider at the clinic (Appendix E).

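### Parents are screened and enrolled after their clinic is randomised, in part by a research assistant who must know the arm, and the primary model adjusts for baseline hesitancy only if a test finds an imbalance

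*Combined protocol and SAP*

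**What the plan says.** Section 11.1 gives the order of events: "enroll and randomize clinics to control and SPARCK arms. We will screen parents for vaccine hesitancy". Each clinic has one arm, so every parent is approached at a clinic whose arm is already set.

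On recruitment, section 13.1 states: "Parents will be approached and screened for this study by a research assistant (RA"), either by telephone (Group Health parents only) or at clinic check-in. In the table in section 5.2 the Parent Eligibility Survey is administered by "Study personnel verbally"; all other parent surveys listed there are self-administered. A parent counts as vaccine hesitant under section 12.1 if she or he meets the rule "defined as ≥2 positive responses on questions 1, 3, 6 and 8 on the eligibility screening survey".

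On what follows enrolment, section 13.1 assigns "the intervention survey at SPARCK clinics (Appendix A) and the placebo survey at control clinics (Appendix B"). When enrolment takes place at the 2 month visit, the assistant "will simply proceed to administer the intervention or placebo survey right after enrollment". The assistant also prints the summary of results and must "hand the printed summary sheet to the child's provider before the visit begins".

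Three other places bear on the point:
- Section 11.4 says that arm allocation will be concealed and that the study will be described in general terms. It does not say from whom allocation is concealed.
- Section 3.7 lists recruitment scripts for both in-person and telephone contact.
- Section 16.1 plans baseline tests between arms, with adjustment in the mixed model for any confounders found to be unbalanced.

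**The concern.** Randomising clinics makes the clinics comparable in expectation. It makes the enrolled parents comparable only if approach, screening and consent work the same way in both arms. Here those steps come after randomisation and, for at least part of the sample, are carried out by someone who knows the arm. Entry depends on two of four spoken attitude answers. The plan itself says, in sections 1.1 and 8.1, that parents have trouble speaking openly about vaccine concerns, so a spoken screen may be sensitive to how it is delivered.

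A difference between arms in whom the assistant approaches, how the items are put, or who consents would change the hesitancy mix of one arm. The plan chose the PACV because it predicts under-immunisation, so a shift in hesitancy would be expected to carry through to the primary outcome and be read as an intervention effect, or hide one.

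**Working it through.** **Who can know the arm**

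| Route | What section 13.1 says | Is knowledge of the arm implied? |
|---|---|---|
| Screened and enrolled in person at the 2 month visit | The enrolling assistant goes straight on to the intervention or placebo survey and delivers the results sheet | Yes, for screening and consent |
| Screened by telephone (Group Health) | An assistant meets the parent at the 2 month visit for consent, then gives the survey | Yes for consent; not stated for the telephone screen |
| Enrolled in person at an earlier visit | An assistant returns at 2 months to give the survey | Not stated; it need not be the same person |

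Section 3.3 divides assistants by health system, not by task or arm. The concealment statement in 11.4 does not name the assistants and cannot hold for those in the first row.

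**How strong the planned safeguard is**

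The plan gives no figure for selection bias, so there is none to reproduce. Take a two-sided 5% baseline t-test on a continuous score with 80 per arm (section 16.2), treating parents as independent:
- Difference detectable with 80% power: (1.96 + 0.84) × √(2/80) = 0.44 SD.
- Power to detect an imbalance of 0.2 SD: 0.2/√(2/80) = 1.26, and Φ(1.26 − 1.96) ≈ 0.24.

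An imbalance of 0.2 SD would therefore go undetected about three times in four.

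**Illustrative size of the bias**

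Inputs from section 16.2: mean 27.1% and SD 33.3 for PACV-SF-positive parents; target 30 days; ICC 0.02; 10 parents per clinic; 80 per arm. Assumptions not in the documents: a share f = 10 to 30% of one arm is wrongly included, and those children have a mean m = 5 to 20% of days under-immunised.

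- Target in points: 30/243.5 = 12.3% of days from birth to 8 months.
- Bias = f × (27.1 − m).
- Design effect: 1 + 9 × 0.02 = 1.18. Standard error of the arm difference: 33.3 × √(2 × 1.18/80) = 5.7 points.
- Type I error (nominal 5%, no true effect): Φ(bias/5.7 − 1.96) + Φ(−bias/5.7 − 1.96).

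| f | m | Bias (points) | Share of 12.3 | Type I error |
|---|---|---|---|---|
| 10% | 20% | 0.10 × 7.1 = 0.7 | 6% | 5.2% |
| 10% | 5% | 0.10 × 22.1 = 2.2 | 18% | 6.7% |
| 30% | 20% | 0.30 × 7.1 = 2.1 | 17% | 6.6% |
| 30% | 5% | 0.30 × 22.1 = 6.6 | 54% | 21% |

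The same inputs give about 58% power for 12.3 points, not the planned 90%. That is a separate matter, and nothing here rests on it.

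**What would produce such an f**

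With hesitancy prevalence p, an excess rate x of non-hesitant parents screening positive in one arm gives f = (1 − p)x / [p + (1 − p)x], so x = fp / [(1 − f)(1 − p)]. This assumes that all hesitant parents screen positive.
- At the 5% Group Health rate in section 16.2: x = 0.005/0.855 = 0.6 points for f = 10%, and 0.015/0.665 = 2.3 points for f = 30%.
- At the original 20% assumption: x = 0.02/0.72 = 2.8 points and 0.06/0.56 = 10.7 points.

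Low prevalence makes the sample sensitive to small differences in screening. It does not show that such differences arise.

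**The case against.** The plan has real protections. Both recruitment routes have scripts, the cut-off is fixed, and parents in both arms hear the same general description of the study. Controls also complete a survey whose results go to the provider, which limits arm-dependent consent on the parents' side. Section 17.6 provides for quarterly review of recruitment and accrual. Nothing gives the assistant a stated reason to favour one arm, and no direction of bias can be derived. All of this stands, and it makes this a risk to manage rather than a demonstrated flaw. It does not remove the risk: a script fixes wording but not whom to approach or how answers are drawn out, and the quarterly review is not described as being by arm.

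A reader might infer that every assistant knows the arm and scores the items. The documents do not support that. Scoring is not described, Appendices F, N and P were not available to check, and knowledge of the arm is unstated for telephone screens. A reader might also infer that no model could repair the problem. That is too strong: a hesitancy covariate corrects measured differences in hesitancy.

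The size is assumed. Neither f nor m has a source in the documents, and the 27.1% mean already includes parents close to the cut-off.

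**Conclusion.** The concern holds as a risk of differential selection. Recruitment follows randomisation, screening is verbal, and for in-person enrolment at the 2 month visit the recruiting assistant must know the arm. The concealment statement cannot cover that assistant. The one analytic safeguard depends on detecting an imbalance that 80 per arm would often miss.

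Under the stated assumptions the bias is about 0.7 to 6.6 points against a target of about 12.3, in either direction. These figures show scale only. The documents do not show that selection differed by arm.

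**What to change.** 1. In section 16.1, prespecify the PACV-SF score from screening as a fixed covariate in the primary mixed model, whatever the baseline tests show. It is collected in both arms before the arm-specific survey, so the cost is one model term. Among the listed evaluations it is the only hesitancy measure common to both arms, because the full PACV is given only in the SPARCK arm.
2. In section 13.1, approach consecutive eligible check-ins. Record and report, by clinic and arm, the numbers approached, screened, hesitant and consented, and the screening route. The cost is a screening log.
3. In section 11.4, state from whom allocation is concealed, whether telephone callers know the arm, and how the screen is scored.

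The covariate has limits. It corrects measured differences in hesitancy only, and if scored as a count of positive answers it takes only the values 2, 3 and 4 among enrolled parents. It does not correct a distorted spoken score or differential consent, which is why the counts by arm are needed.

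Self-completed screening on the study iPad is optional. It would make screening mode differ between in-person and telephone parents, and clinics are paired on vaccine doses ordered, not on health system, so mode could become unbalanced between arms.

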**Version Date: 5/1/2018** 

will simply proceed to administer the intervention or placebo survey right after enrollment. The RA will generate and print an automated summary sheet of the parent's screening results, and hand the printed summary sheet to the child's provider before the visit begins (Appendices C and D). They will also alert the provider that their patient is a SPARCK study participant by writing, "SPARCK STUDY" in the scheduling notes section of the child's electronic health record. This process will be repeated before the child's 6 month health supervision visit. After their child's 6 month health supervision visit, parents will complete a survey about their satisfaction with their child's provider at the clinic (Appendix E).

## 14. Study Evaluations

This section should list the details of all of the measurements, procedures, laboratory tests, etc. that are included in the Table of Evaluations including where they will be performed. Example: Hematology testing includes Complete Blood Count with differential performed in the Seattle Children's lab. In particular, non-standard tests should be described including specific sample collection information.

Information in this section can also be summarized in a table, or appended to the Table of Evaluations.

## 14.1. **Describe study evaluations.** Study evaluations are:

- 1. SPARCK Intervention Survey (Appendix A)
- 2. SPARCK placebo survey (Appendix B)
- 3. Parent post-visit satisfaction survey (Appendix E)
- 4. PACV-Short form screening survey (Appendix F)
- 5. Parent demographic survey (Appendix G)
- 6. Provider baseline survey (Appendix K)
- 7. Provider follow-up survey (Appendix L)
- 8. Child's vaccination status by age 8 months

## 15. Risks and Benefits

#### **Potential Risks**

#### 15.1. Describe the potential risks associated with this research.

Parent/Child: Parents being recruited for the study may experience anxiety or discomfort because they do not meet inclusion criteria. Enrolled parents may experience anxiety or discomfort from having to complete questionnaires. In addition, participation in the project might be associated with some risks such as confusion about or disruption in the parent-provider relationship. In particular, parents may be concerned that their answers to the previsit screening questions might hurt their relationship with their child's doctor. Alternatively, they may feel inconvenienced by having to discuss their responses with their child's doctor. In total, however, the risks to parents and their children who participate in this study are minimal and are not greater in and of themselves than those ordinarily encountered in daily life or during the performance of routine physical or psychological examinations or tests.

Study Title: Screening Parents about Recommended

Care for Kids (SPARCK) Study

Principal Investigator: [name], MPH

**Version Date: 5/1/2018** 

Providers: The main risk for providers in the study is the possibility of information on the immunization status of their child patients and/or parent-ratings of their vaccine discussions will be revealed to their colleagues, patients, or the public at large. Another risk is disruption in the parent-provider relationship. In particular, disclosure to providers of a parent's overall vaccine hesitancy or specific vaccine concerns may highlight disagreements between provider and parent and lead to a difficult conversation during the visit. In total, however, the risks to providers who participate in this study are minimal and are not greater in and of themselves than those ordinarily encountered in daily life or during the performance of routine physical or psychological examinations or tests.

## **Investigator Help**

## **Protection Against Risks**

15.2. Describe how the study design will prevent or minimize any potential risks or discomfort. Pease explain what steps you will take to minimize risks of harm and protect participants' rights and welfare. If the study procedures or intervention may pose possible harms to study team, family members or others, please also discuss methods of reducing risks here.

Parent/Child: Data kept for research evaluation purposes on parents and children will be de-identified with linking information kept in separate files. Only Group Health and Seattle Children's study staff will have access to the linked file with identifying information for the purposes of conducting research. No individual parent or child data will be publicly reported and no individual will be identified in any published findings, with all study results analyzed and presented only at the aggregate level.

Drs. [name] and [name] will provide oversight for the collection, management and protection of study data. Data collected from Group Health parents will be securely stored at GHRI. Data collected from non-Group Health parents will be securely stored at SCRI. To ensure confidentiality and protection of the data, we will use the following strategies: 1) we will create a unique study ID for each participant in the study; 2) de-identified data will be placed on a secure, password-protected file transfer protocol server; and 3) all linkages between the unique study ID and the individual-level data will be destroyed 5 years after the completion of the study. We will adhere to all HIPAA requirements as required by the law. For Group Health parents, identifiable data will be stored in the GHRI Data Warehouse where access is limited to GHRI study staff, and data are backed up automatically at least nightly. For non-Group Health parents, data will be stored at SCRI where access is limited to SCRI study staff and data are backed up automatically at least nightly. We will maintain each dataset separately and index the records using unique encrypted identifiers to facilitate linkages between files while maintaining confidentiality of personal health information. Only de-identified data from Group Health will be sent to SCRI investigators for analysis.

Providers: No individual provider data will be publicly reported and no individual will be identified in any published findings, with all study results analyzed and presented only at the aggregate level. All survey data will be confidential. These data files will only contain a unique study ID for each survey and no direct identifiers. The electronic survey data files

Study Title: Screening Parents about Recommended

Care for Kids (SPARCK) Study

Principal Investigator: [name], MPH

**Version Date: 5/1/2018** 

will be stored at Seattle Children's Research Institute where access is limited to study staff.

#### **Potential Benefits**

15.3. Describe potential benefits associated with this research.

Parent/Child: Parents will receive a \$10 gift card upon enrollment and a \$15 gift card after completing the 4 and 6 month surveys to thank them for their time. Parents might also benefit from improved provider-parent communication by having their attitudes regarding preventive care topics explicitly solicited and conveyed to their child's provider. In the face of these potential benefits, the risks to study subjects, which themselves are minimal, seem reasonable.

Providers: There is no direct benefit for providers who participate in the study. Participating providers, however, may benefit from pre-visit knowledge of parental preventive care concerns if it increases parental satisfaction by reducing parental unmet concerns. In the face of these potential benefits, the risks to study subjects, which themselves are minimal, seem reasonable.

#### 16. Statistical Considerations

This section should provide sufficient detail to permit assurance that the sample size is justified and the statistical methods sufficient and appropriate for the research question(s).

#### **Analysis Plan and Statistical Methods**

16.1. Outline the data analysis plans relating to each specific aim/objective or research hypothesis mentioned in section 11 above. It should be clear how the analysis results will allow each aim/objective to be answered. The analysis plans for the primary aim should be detailed. Analysis plans for secondary aims may be brief, but must be included. Give the names of specific statistical methods and state which variables will be used with them.

Aim1: To evaluate the effectiveness of the SPARCK intervention in increasing vaccine acceptance. We will conduct an intention-to-treat analysis for Aim 1. Parents will be the unit of analysis. We will examine baseline characteristics among control and SPARCK parents using Pearson's  $\chi 2$  tests (or Fisher's exact tests) for categorical variables and t-tests for continuous variables to assess for any unbalanced confounders between control and SPARCK arms. To compare our primary outcome of percent days underimmunized between control and SPARCK arms, we will apply linear mixed effects regression modeling to the percent days under-immunized with clinic-specific random-effects to account for within-clinic correlation. If unbalanced confounders are detected between arms, they will be adjusted for in the mixed effects models.

Aim 2: To assess how parent-rated experience of the vaccine discussion changes as a function of the SPARCK intervention. For Aim 2, we will use Pearson's χ2 test to compare parent (binary) ratings of their vaccine discussion between control and SPARCK

Study Title: Screening Parents about Recommended

Care for Kids (SPARCK) Study

Principal Investigator: [name], MPH

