#### The specific aims of this project are as follows:

Aim 1: Evaluate the impact of the SPARCK intervention on a child's immunization status. We will use a matched-pair, cluster randomized controlled trial design in which we assign up to 30 primary care clinics in the Seattle area and within the Group Health healthcare delivery system in Western Washington to a control arm or the SPARCK arm and enroll 160 vaccine-hesitant parents whose newborns receive health supervision at study clinics.

Aim 2: Assess how parents' ratings of their vaccine discussions with their child's provider change as a function of the SPARCK intervention. This will be accomplished by

Study Title: Screening Parents about Recommended

Care for Kids (SPARCK) Study

Principal Investigator: [name], MPH

Version Date: 5/1/2018

assessing parent visit satisfaction with a questionnaire after their child's 6 month health supervision visit.

Aim 3: Compare pre- and post-study perceptions of barriers to quality vaccine discussions with parents between providers in the SPARCK and control arm. This will be accomplished by having providers complete a survey assessing their perceptions of specific barriers to quality preventive care discussions with parents before the study begins and then again after the study ends.

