#### Randomization Method and Blinding

11.4. Describe the randomization method and blinding (if applicable).

Among interested Seattle area primary care practices and 21 Group Health primary care clinics in 5 western Washington counties (King, Snohomish, Pierce, Thurston, and Kitsap), we will pair clinics based upon the number of vaccines doses ordered in the prior year and subsequently enroll and randomize up to 30 to the control and SPARCK intervention arms. We will conceal study arm allocation and describe the study generally as one that seeks to determine the impact of soliciting parent attitudes regarding preventive care topics before health supervision visits on improved health outcomes.

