**Version Date: 5/1/2018** 

arms. We will apply mixed effects logistic regression model to this outcome to account for within-clinic correlation and any unbalanced parent confounding factors. When summarizing parent experience as a continuous variable, we will apply Box-Cox transformation if it is highly skewed and linear mixed effect models to examine the differences in parent experience between control and SPARCK arms.

Aim 3: To characterize the effect of the SPARCK intervention on provider perceptions of barriers to quality vaccine discussions. For Aim 3, providers will be the unit of analysis. We will compare the pre- and post-study proportions of control and SPARCK providers reporting that time, understanding of specific parental vaccine concerns, and knowledge of overall parental vaccine attitudes were significant barriers (defined as 4 or 5 on a 1-5 scale) to quality vaccine discussions. We will use t-tests for an unadjusted analysis of the pre-post differences between control and SPARCK arms and multivariate linear regression for adjusted analyses that control for potential confounding variables such as provider demographic and practice characteristics.

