## 16.2. Provide a justification for the sample size and power calculations.

Based on preliminary data, children of parents with a positive PACV-SF had a mean percentage of days under-immunized of 27.1% (standard deviation [SD] 33.3) from birth to 8 months of age for 4 vaccines combined (hepatitis B, DTaP, Hib, and IPV). To be able to detect with adequate power (90%) a decrease in under-immunization of 30 days per vaccine—a decrease that has the potential to be clinical meaningful since it equals the 1 month recommended interval a parent has before their child is considered late for a vaccination dose—we need to enroll 160 parent/newborn pairs total, with 80 per arm and 10 at each of the 16 study clinics (assuming an  $\alpha$  of 0.05 and an intraclass correlation coefficient for within-clinic correlation of 0.02).

In our original calculation, we assumed 80% of GH parents would be reached, a conservative estimate of a 20% prevalence of GH parents who will have a positive PACV-SF, 10% of VHPs who fail to meet other study eligibility requirements, 25% of VHPs who do not agree to participate (unpublished data), a 10% attrition rate over the course of the study, and 70% who remain continuous GH members, resulting in the need to approach 2400 parents to reach our sample size goal. From 2010 – 2012, there was an average of 2679 GH births per year in the 5 Washington State counties from which we will recruit parents. Reaching our sample size goal should therefore be feasible given our designated 15 month recruitment period. However, we now know that the vaccine hesitancy rate at GH is about 5%. Therefore, we need to screen approximately 3500 parents to reach the desired sample size goals of 160.

For Aim 2, we will have 80% power with a sample size of 160 parents to detect a 17% increase in the proportion of parents who rate their visit highly, assuming a baseline proportion of 72%.  For Aim 3, we will have 80% power to detect a 14% pre-post difference in the proportion of providers who perceive time as a barrier to quality vaccine discussions between control (1% pre-post difference) and SPARCK arms (15% pre-post difference), assuming a baseline proportion of 62% and 56 providers in each arm.

Study Title: Screening Parents about Recommended

Care for Kids (SPARCK) Study

Principal Investigator: [name], MPH

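### Clinics are randomised in pairs matched on vaccine doses ordered, but the Aim 1 and Aim 2 mixed models contain neither the pair nor doses ordered, so some precision is lost to the extent that doses ordered predicts the outcome

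*Combined protocol and SAP*

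**What the plan says.** - Design. Section 1.1, Aim 1: "We will use a matched-pair, cluster randomized controlled trial design". Section 11.4 names the matching variable: "we will pair clinics based upon the number of vaccines doses ordered in the prior year". Section 11.1 also describes pairing on doses ordered, followed by randomisation.
- Aim 1 analysis (Section 16.1): "we will apply linear mixed effects regression modeling to the percent days under-immunized with clinic-specific random-effects to account for within-clinic correlation". The only way in for a covariate is conditional: "If unbalanced confounders are detected between arms, they will be adjusted for in the mixed effects models". The preceding baseline comparison is between the parents in the two arms.
- Aim 2 analysis (Section 16.1): "We will apply mixed effects logistic regression model to this outcome to account for within-clinic correlation and any unbalanced parent confounding factors". If parent experience is summarised as a continuous score, a linear mixed model is planned, again without a matching term. A Pearson chi-square test is listed as well.
- Sample size (Section 16.2): 160 parents, "with 80 per arm and 10 at each of the 16 study clinics", with an ICC of 0.02. No correlation within pairs enters the calculation.

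**The concern.** Pairing makes the two arms alike on doses ordered. If doses ordered is related to the outcome, differences between pairs largely cancel out of the arm difference. A model whose only cluster term is a clinic random effect does not know this. It estimates the full between-clinic variance and puts all of it into the standard error.

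The rule for unbalanced confounders is unlikely to repair this. It looks at parent characteristics, whereas doses ordered belongs to the clinic, and the better the matching, the more balanced that variable will look.

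At stake is precision: a confidence interval somewhat wider than it need be, and a test with somewhat less power than the design could give.

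**Working it through.** **Inputs from Section 16.2.** SD 33.3; ICC 0.02; 16 clinics of 10, so 8 pairs; target difference 30 days per vaccine; alpha 0.05.

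**Assumptions.** Two-sided test. Birth to 8 months taken as 243 days, so the target is 30/243 = 12.35 points. The share f of between-clinic variance explained by doses ordered is not in the documents, so the range 0 to 1 is shown.

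**Step 1: the plan's own figure.** Without clustering, n per arm = 2(1.960 + 1.282)² × 33.3² / 12.35² = 153. The design effect is 1 + 9 × 0.02 = 1.18, which gives 181 per arm against the stated 80. With 80 per arm, power is Φ(12.35/5.72 − 1.96) = Φ(0.20) = 58%, not 90%. That mismatch depends on the assumed window and is a separate matter. It is shown only because it explains why the powers below start near 56%.

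**Step 2: variance components.** Between clinics: 0.02 × 33.3² = 22.18. Within clinics, per clinic mean: 0.98 × 33.3² / 10 = 108.67.

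**Step 3: standard error of the arm difference.**
- Planned model: √[2(22.18 + 108.67)/8] = 5.72.
- Respecting the matching: √[2((1 − f) × 22.18 + 108.67)/8].

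The planned model's 95% half-width is 2.145 × 5.72 = 12.27 (t, 14 df). The last column is for the model with doses ordered as a covariate (t, 13 df).

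| f | SE respecting matching | Planned SE too large by | Half-width with covariate |
|---|---|---|---|
| 0 | 5.72 | 0% | 12.36 |
| 0.25 | 5.60 | 2.2% | 12.09 |
| 0.5 | 5.47 | 4.5% | 11.82 |
| 0.75 | 5.34 | 7.0% | 11.54 |
| 1 | 5.21 | 9.7% | 11.26 |

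**Step 4: simulation.** At least 100,000 trials per setting, REML with the clinic variance truncated at zero, test at 1.96, ICC 0.02.

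| f | Null rejection, planned model | Power, planned → with covariate |
|---|---|---|
| 0 | 5.1% | 55.9% → 55.7% |
| 0.25 | 4.8% | 56.1% → 57.1% |
| 0.5 | 4.2% | 55.8% → 58.2% |
| 1 | 3.3% | 55.9% → 61.1% |

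At f = 1 the mean model SE is 5.86 against a true SD of 5.21. Part of that gap is due to truncation, since at f = 0 the mean SE is 5.86 against a true SD of 5.71. The matching part is 5.71/5.21 = 1.096, in line with the 9.7% in Step 3.

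**Step 5: other settings.**
- With 30 clinics (15 pairs, 160/30 = 5.33 parents each), the largest possible excess in the SE falls from 9.7% to 5.3%.
- With an assumed ICC of 0.05 and 8 pairs, the excess is 9.9% at f = 0.5 and 24% at f = 1. Power rises from 49% to about 55% and from 48% to 62%.

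**Step 6: other ways to use the pairing (8 pairs, ICC 0.02 unless stated).**
- A strict paired analysis has 7 df instead of 14. It narrows the interval only if the correlation within pairs exceeds 1 − (2.145/2.365)² = 0.177. The most that can occur is 22.18/130.85 = 0.169, so even at f = 1 the half-width is 12.33 against 12.27.
- A random pair intercept tested at 1.96 rejects a true null 6.0% of the time at f = 0 and 5.2% at f = 0.5. At an assumed ICC of 0.05 these become 7.4% and 5.8%.

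**The case against.** The strongest reply is that a random-clinic analysis of a matched design is valid: the estimate is unbiased and, at the plan's ICC, the error is on the cautious side. The gain there is 1 to 5 power points, less with 30 clinics. Doses ordered measures clinic volume, and nothing in the documents shows that volume predicts under-immunization among hesitant parents. The simulation also lets the covariate capture the pair effect exactly, which a real clinic variable on a chosen scale will not do. All of this stands. It limits the weight of the point but does not remove the omission.

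Three stronger readings are tempting, and the documents do not support them.

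- A reader might infer that the error bars are too wide whenever the matching works. At an assumed ICC of 0.05, the planned test at 1.96 rejects 5.1% under the null when a quarter of the between-clinic variance is explained, and 5.7% when a tenth is. Partly effective matching does not make that test conservative there.
- A reader might take a gain such as 48% to 62% as the expected benefit. It needs an ICC of 0.05, which the documents do not give, and full explanation by doses ordered. Part of any gain at that ICC may also be inflated error: at f = 0.5, null rejection goes from 4.1% to 5.3% when the covariate is added and the test stays at 1.96.
- A reader might carry the figures over to Aim 2. No Aim 2 magnitude is computed here. The Aim 2 chi-square ignores clinics altogether, so with weak matching its standard error is too small, by a factor of about √1.18 = 1.09. That is a separate matter and runs in the opposite direction.

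**Conclusion.** The point holds as a modest loss of precision. The matching factor is used in the design and appears in none of the Aim 1 or Aim 2 mixed models, and the confounder rule would not normally bring it in. For Aim 1 at ICC 0.02 with 8 pairs, the standard error is too large by 4.5% if doses ordered explains half of the between-clinic variance and by 9.7% at the ceiling. If doses ordered explains nothing, nothing is lost. These figures rest on the 243-day window (for power), equal clinic sizes and an unknown share explained. The omission itself is certain from the text; its practical importance is not. The change is worth making because it costs almost nothing and should be fixed before results are seen.

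**What to change.** In Section 16.1, state that the Aim 1 and Aim 2 mixed models will include vaccine doses ordered in the prior year, for example on the log scale, as a fixed clinic-level covariate whatever the baseline comparisons show. State also that the linear mixed models will use a small-sample degrees-of-freedom correction (for example Kenward–Roger).

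Do not fit pair as a fixed effect: with 8 pairs it would use 7 of the 14 clinic-level degrees of freedom. Do not use a random pair intercept without a small-sample correction.

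The cost is one sentence. The variable must already be held for every clinic in order to pair them. Adjustment uses one clinic-level degree of freedom and loses about 0.5 point of power or less if the matching proves uninformative, comparing like with like. The correction has its own price: by formula, the unadjusted model's power is 58% with 1.96 and 52% with t on 14 df. That comes from having 16 clinics and is not a cost of the covariate.
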